24.0 Provisions to Protect the Privacy Interests of Participants*

24.1 Only IRB approved members of the study team will be granted access to the study folder located on the network drive or the REDCap database, which is password protected and encrypted. Additionally, study team members who are responsible for collected data only will be granted limited access to REDCap, allowing them to record data only.

24.2 PHI to be accessed and/or recorded for this research study includes: DOB, MRN, dates of service (AXR and BUS exams, dates and dates of severity milestones and death if applicable) will be recorded.

25.0 Withdrawal of Participants*

25.1 A subject may be withdrawn from participation if they were transferred to another outside hospital or if they undergo exploratory laparotomy with ostomy and mucus fistula creation during the course of their admission as this procedure can preclude them from safely undergoing a BUS.

25.2 Subjects may also be discontinued from the study at the discretion of the site investigator as deemed appropriate for any reason.

25.3 If a subject withdraws from the research study, data that has already been collected may still be used; however, no new information will be collected except information related to adverse events or other safety issues.

DATA MANAGEMENT

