10.2 Randomization

Infants who meet inclusion criteria of NEC concern as above will be randomized to either AXR arm or AXR + BUS arm based on the calendar month the infant was born. A pre-generated randomization calendar will be posted in the NICU workroom to inform the care team which arm the infant will be randomized to, and consequently which imaging test will be ordered.

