10.6 Follow-up imaging

Infants with suspected NEC may need additional follow-up imaging for ongoing concerns of NEC. If the treating neonatologist deems follow-up imaging is needed, study infants will continue to have either AXR or AXR + BUS performed as determined by their randomization arm.

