12.0 Follow-up

- All study infants will be followed throughout their course in the NICU, from admission to discharge. All data will be collected through clinical chart review. Follow-up will end once infants are discharged from the NICU. We will collect the following data points: (1) baseline characteristics (gestational age, birth weight, sex, race, mode of delivery, Apgar scores; (2) clinical characteristics at time of NEC concern (clinical presentation, age at time of NEC concern, results of diagnostic tests for NEC concern, information on treatment including days to full enteral feeds and days on antibiotics); and clinical outcomes at discharge (total length of stay, age at discharge, co-morbidities during NICU admission).

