26.0 Data Collection*

26.1 The study will collect baseline clinical characteristics, lab test results, AXR and BUS results, clinical diagnosis, treatment data, and survey results.

- Clinical characteristics: gestational age at birth, weight at birth, sex, race/ethnicity, age at time of NEC concern,
- Lab test results: complete blood cell count (CBC), C-reactive protein (CRP), blood culture
- AXR and BUS results: time of order input in the chart, time of image acquisition, time of reporting, text of report and interpretation by radiologist
- Clinical diagnosis: NEC, no NEC, food protein-induced enterocolitis, clinical sepsis, other diagnosis

- Treatment data: medical treatment of NEC including days of bowel rest, days to full enteral feeds, days on antibiotics; surgical treatment of NEC including peritoneal drainage or exploratory laparotomy
- Survey results: post-AXR survey and post-BUS survey by neonatologists

26.2 Data will be obtained from the electronic medical record and surveys/questionnaires.

26.3 Sensitive Data: We will not be collecting or accessing sensitive data.

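### As worded, sections 25.1 to 25.3 can end outcome collection after ostomy surgery, against 12.0, 26.1 and intention-to-treat; 28.1 also lacks a workable rule for infants who die or have no full-feeds date

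*Combined protocol and SAP*

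**What the plan says.** **Withdrawal (25.0).** Under 25.1 an infant may be withdrawn on transfer to an outside hospital, or "if they undergo exploratory laparotomy with ostomy and mucus fistula creation during the course of their admission". The reason given for the surgical ground is "as this procedure can preclude them from safely undergoing a BUS". Section 25.2 adds discontinuation "at the discretion of the site investigator as deemed appropriate for any reason". Under 25.3, data already collected may be used after withdrawal, but "no new information will be collected except information related to adverse events or other safety issues".

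**Follow-up and data.** Section 12.0 says: "All study infants will be followed throughout their course in the NICU, from admission to discharge". It adds that all data come from chart review. Section 26.1 lists days of bowel rest, days to full enteral feeds and days on antibiotics, and also "surgical treatment of NEC including peritoneal drainage or exploratory laparotomy".

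**Arms.** Under 10.2 the randomisation calendar is "posted in the NICU workroom to inform the care team which arm the infant will be randomized to". Under 10.6, when follow-up imaging is needed, "study infants will continue to have either AXR or AXR + BUS performed as determined by their randomization arm".

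**Analysis.** Section 28.1 compares durations, including days to full feeds, by Student's t-test. It also plans a Kaplan-Meier curve of time to full feeds, censored at death, discharge or transfer, or 30 days after the first NEC concern. Patient outcomes are to follow intention-to-treat. Section 28.3 sizes the trial on the difference in mean days to full feeds. Section 24.2 includes dates of death among the recorded data.

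**The concern.** The ground for withdrawal after ostomy concerns scanning. The outcomes come from the chart, which stays available while the infant is in the NICU. No section separates stopping BUS from stopping follow-up, so a site that follows 25.1 and 25.3 literally would stop recording feeding, bowel-rest and antibiotic outcomes in some of the sickest infants.

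The trigger occurs after randomisation, the care team knows the arm, and only AXR + BUS infants are assigned follow-up BUS. A scanning-safety reason therefore bears mainly on one arm. If infants with ostomies were withdrawn more often there, that arm's mean would lose slow feeders, and BUS could seem to shorten time to full feeds when it does not. This is the outcome on which the trial is sized.

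Two gaps in 28.1 touch the same infants. An infant who dies cannot reach full feeds, yet death is treated as ordinary censoring. The t-test has no rule for an infant without a full-feeds date, whether through death, transfer, withdrawal or never reaching full feeds. The censoring rule, including its handling of transfer and day 30, is stated for the curve only, and withdrawal is not among its censoring reasons.

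**Working it through.** **1. The sections side by side.**

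| Question | 25.1 to 25.3 | Elsewhere |
|---|---|---|
| Who is followed to discharge? | Not those withdrawn, if 25.3 covers withdrawal by the team | All study infants (12.0) |
| What is collected after ostomy surgery? | Safety information only | Bowel rest, antibiotics, days to full feeds (26.1) |
| Who is analysed? | Those with data up to withdrawal | Intention-to-treat (28.1) |

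The laparotomy itself is known before any withdrawal, so the conflict with 26.1 concerns only what follows surgery.

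**2. The plan's own sample size.** Normal approximation, two-sided 0.05, 80% power, arms assumed equal (no ratio is stated): total N = 4 × [SD × (1.960 + 0.842) / difference]². For 5 days and SD 8: 4 × (8 × 2.802 / 5)² = 80.4, rounded up to 81, as in Table 1. The other cells also reproduce. The formula has no allowance for missing outcomes.

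Power for N observed values is Φ(5√N / 16 − 1.96):

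- No loss, N = 81: Φ(0.85) = 80%.
- 10% loss, N = 72.9: Φ(0.71) = 76%.
- 20% loss, N = 64.8: Φ(0.56) = 71%.

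**3. Illustration of unequal withdrawal.** From 28.3: mean 16, SD 9 days. Assumed, because the documents give no rates: gamma feeding times, 5% deaths, 5% ostomy (about 2 infants per arm at 81), no true difference, one episode per infant. Full feeds after ostomy are uniform over days 28 to 60 (mean 44) or, in brackets, days 20 to 40 (mean 30). The t-test uses infants with an observed date.

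If every infant with an ostomy is withdrawn in AXR + BUS and none in AXR, the AXR mean exceeds the other by (0.05 / 0.95) × (44 − 16) = 1.5 days [(0.05 / 0.95) × (30 − 16) = 0.7].

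At 75% vs 25% withdrawn, the ostomy shares left are 0.0125 / 0.9125 = 0.014 in AXR + BUS and 0.0375 / 0.9375 = 0.040 in AXR. The gap is 0.026 × 28 = 0.7 days [0.026 × 14 = 0.4].

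Simulated false-positive rates (20,000 trials per scenario; a repeat run agreed to within about one percentage point):

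| Withdrawal after ostomy | False gain, days | 81 episodes | 200 infants (8.0) |
|---|---|---|---|
| AXR + BUS only (extreme) | 1.5 [0.7] | 8 to 9% [6 to 7%] | 16% [8 to 9%] |
| 75% vs 25% | 0.7 [0.4] | 6% [5%] | 7 to 8% [6%] |
| Equal | 0 | 5% | 5% |

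**4. Censoring death.** With gamma times, mean 16 and SD 9, the share reaching full feeds by day 30 among infants who do not die is 0.923. If deaths come before full feeds, the true share is (1 − death rate) × 0.923, while the Kaplan-Meier estimate stays near 92%:

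- Deaths 2%: 0.98 × 0.923 = 90.5%.
- Deaths 5%: 0.95 × 0.923 = 88%.
- Deaths 10%: 0.90 × 0.923 = 83%.

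With deaths of 8% vs 5%, both curves still read 92%, but the true shares are 0.92 × 0.923 = 85% and 88%. The means of infants reaching full feeds are 16.0 in both arms, so neither analysis shows the difference.

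**5. Infants past day 30.** The same distribution leaves 1 − 0.923 = about 8% not on full feeds at day 30 even without deaths (6% under a normal distribution). Whether and how their later dates enter the t-test is not stated.

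**The case against.** **Section 25.3 may not apply.** It speaks of a subject who withdraws, whereas 25.1 and 25.2 speak of infants withdrawn or discontinued by the team. Read narrowly, 25.3 covers only families, 12.0 governs the rest, and there is no conflict. Section 25.1 is also permissive. Both points stand: the loss is possible, not certain. But 25.3 directly follows two team-initiated grounds and draws no distinction, and parental permission is waived, so two sites could reasonably apply it differently.

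**Unequal withdrawal is assumed.** Section 25.1 covers both arms, and no rate is given. A reader might infer that the plan builds in a bias favouring BUS. The documents do not support that: they give one arm a stronger reason for withdrawal, not evidence that it would occur more often there. At 81 episodes and 75% vs 25%, false positives are only 5 to 6%.

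**Censoring death is an explicit choice.** This is correct; it contradicts nothing. With equal deaths both curves shift together, so the comparison is not biased. What stands is that the curve misstates the share reaching full feeds and would hide a difference in deaths.

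**The t-test should stay.** A reader might conclude that a competing-risks test must replace it as the main comparison. That does not follow: 28.3 sizes the trial on means, and changing the test would be a debatable trade-off in power and in which days carry weight.

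**Conclusion.** The concern holds as a conflict of wording with a possible informative loss of outcomes, plus an incomplete analysis rule. As written, and unless 25.3 is limited to withdrawal by families, outcome collection can stop after ostomy surgery for a reason that concerns scanning only.

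The likely size is modest. At an assumed 5% ostomy and 81 episodes, the extreme case moves the false-positive rate from 5% to 6 to 9%, a milder imbalance barely moves it, and equal withdrawal leaves no between-arm bias, though infants who had surgery would still be missing from both arms. These figures rest on assumed rates and feeding times. Overstatement by the Kaplan-Meier curve is about 4 points at an assumed 5% deaths.

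This should be fixed, because the conflict touches the sizing outcome, the remedy is cheap, and outcomes not collected under 25.3 may not be usable later. The documents do not show that the trial's comparison would be invalid.

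**What to change.** 1. **Reconcile 25.1 to 25.3 with 12.0, 26.1 and 28.1.** State that ending study BUS does not end chart-based outcome collection, which continues to NICU discharge in the randomised arm, under the same rule in both arms. Say whether 25.3 covers withdrawal by the team. Whether BUS is done after ostomy is a clinical matter for the sponsor and is not addressed here.
2. **Complete 28.1.** Show time to full feeds as cumulative incidence with death as a competing event, in place of or beside the Kaplan-Meier curve. Report deaths, ostomies, transfers and withdrawals by arm. Keep the t-test as the comparison on which 28.3 sizes the trial, and state how infants without a full-feeds date enter it: death, transfer, withdrawal, never reached. A Gray's test is optional.
3. **Add a note to 28.3.** Table 1 assumes complete data. At 81 episodes, 5 days and SD 8, power falls from 80% to about 76% at 10% loss and 71% at 20%.

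**Cost.** Wording and a little analysis work. No new data are needed: chart review to discharge is already planned and dates of death are recorded. The real cost may be power. If the pilot SD excludes surgical episodes, adding 5% ostomies at days 28 to 60 widens an SD of 8 to √(0.947 × 64 + 0.053 × 85.3 + 0.053 × 0.947 × 28²) = about 10.2, where 85.3 = 32² / 12 is the variance of the post-ostomy times. Simulated t-test power for 16 vs 11 days at 81 episodes is then 50 to 52% with these infants kept (65 to 66% if full feeds come at days 20 to 40), against 75 to 76% with them dropped. If the pilot SD already includes surgical episodes, these figures count the slow feeders twice and are too pessimistic. The documents do not say which applies, so the size of the loss is uncertain.

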26.0 Data Collection*

26.1 The study will collect baseline clinical characteristics, lab test results, AXR and BUS results, clinical diagnosis, treatment data, and survey results.

- Clinical characteristics: gestational age at birth, weight at birth, sex, race/ethnicity, age at time of NEC concern,
- Lab test results: complete blood cell count (CBC), C-reactive protein (CRP), blood culture
- AXR and BUS results: time of order input in the chart, time of image acquisition, time of reporting, text of report and interpretation by radiologist
- Clinical diagnosis: NEC, no NEC, food protein-induced enterocolitis, clinical sepsis, other diagnosis

- Treatment data: medical treatment of NEC including days of bowel rest, days to full enteral feeds, days on antibiotics; surgical treatment of NEC including peritoneal drainage or exploratory laparotomy
- Survey results: post-AXR survey and post-BUS survey by neonatologists

26.2 Data will be obtained from the electronic medical record and surveys/questionnaires.

26.3 Sensitive Data: We will not be collecting or accessing sensitive data.

27.0 Adverse Events and Unanticipated Problems*

27.1 Monitoring: The study team will meet bi-weekly to monitor study progress, review participants and data, and troubleshoot any questions or problems related to the study. As all study interventions are standard of care, we do not anticipate any adverse events or problems related to the study protocol or add-on BUS.

27.2 Reporting: We confirm that Policy 5.11 Reportable Events of the CM Research Program Policies and Procedures will be followed in regard to reporting adverse events and other unanticipated problems to the CM IRB.

28.0 Statistical Analysis*

28.1 We will use two-tailed McNemar's test with paired measures to analyze differences in diagnostic thinking efficacy and therapeutic efficacy from pre- and post-BUS surveys. Comparison of duration of antibiotics, bowel rest, and days to full enteral feeds will be performed using Student's t-test. Kaplan-Meier curve will be used to analyze time to full feeds between the 2 groups, censoring for death, discharge/transfer out of the hospital, or 30 days following initial NEC concern. Analyses of patient outcomes (duration of bowel rest, duration of antibiotics, time to full feeds) will follow the intention-to-treat principle, with statistical significance set at a P value of < 0.05.

28.2 We will use t-test to analyze differences in mean time of BUS image acquisition and reporting. Chi-square test will be used to compare differences in proportion of BUS studies that were performed and reported per standardized protocol. Inter-rater reliability for BUS studies will be assessed by Cohen's kappa statistics.

28.3 Sample size was calculated based on our pilot study which demonstrated a mean \pm SD of duration to full enteral feeds of 16 ± 9 days per episode of NEC concern. Using this information, we generated Table 1, which shows sample sizes for a range of possible means and standard deviations, with significance level of 0.05 and 80% power. For a 1-year study with 67 to 81 distinct episodes, for an SD of +8 days, we anticipate having sufficient sample size to detect a 5- to 6-day difference in mean duration to full feeds (highlighted in gray in Table 1).

Difference of means between groups	Expected Standard Deviation		
	± 8	± 9	± 10
4 days	126	160	198
5 days	81	102	126
6 days	56	72	88

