1.0 Study Summary*

The diagnosis of necrotizing enterocolitis (NEC) – an acute and life-threatening intestinal disease that affects 5-10% of infants – can be challenging. Traditionally, neonatologists rely on abdominal radiographs (AXR) to evaluate infants with concern for NEC. In recent years, bowel ultrasound (BUS) has been proposed as a helpful adjunct to AXR for NEC evaluation. In centers where BUS expertise is available, clinicians now have the option of using BUS in addition to AXR in their diagnostic evaluation for NEC. However, significant variability remains on whether neonatologists would use or not use BUS in this clinical setting. An important reason for this variability is the lack of evidence regarding whether BUS improves patient outcomes or not. Additionally, BUS expertise generally is available only in highly specialized children's hospitals. Thus, in centers with limited BUS availability, AXR remains the standard imaging modality for NEC. ***The lack of rigorous and robust clinical trials conducted in diverse NICU settings is an important gap in knowledge that needs to be addressed before the routine use of add-on BUS for NEC evaluation.***

To help address these limitations, we propose to conduct comparative effectiveness research to evaluate the benefits of add-on BUS on patient outcomes. Our study design will be a pragmatic randomized clinical trial (RCT) of AXR versus AXR + BUS in infants with suspected NEC. We propose to conduct this study in two diverse sites. The first site will be the level IV NICU of Children's Mercy Kansas City (CMKC), which already has expertise in BUS for NEC. The second site will be the level III NICU of University of Kansas Medical Center (KUMC), an adult hospital with less experience in BUS. The rationale for this study is that infants at high risk for NEC are cared for in diverse settings including level III NICUs in adult hospitals that have little experience in using BUS to evaluate NEC. Our study has two specific aims.

Specific aim #1: To determine the impact of add-on BUS for NEC evaluation on patient outcomes in two different NICU settings. We hypothesize that adding BUS to NEC evaluation changes differential diagnosis, therapy plan and patient outcomes.

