10.9 Blood and Other Specimen Collection: NA

11.0 Surveys and Psychometric Testing:

- We will conduct two surveys to determine change in clinician's diagnostic and therapeutic thinking. The first survey (post-AXR survey), applicable to all infants, will be conducted after AXR is performed. The second survey (post-BUS survey), applicable only to infants randomized to AXR + BUS, will be conducted after BUS is performed. Surveys will be answered by the neonatologist taking care of the infants using a 5-point Likert scale from "not at all likely" to "extremely likely".

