32.0 Setting & Locations*

32.1 The NICU at CMKC is an 87-bed level IV NICU. Majority of infants admitted at the NICU are born at other hospitals and are typically transferred to CMKC due to need for specialized care. Neonatologists are in-house 24/7. As a children's hospital, radiology staff at CMKC are composed of pediatric sonographers and pediatric radiologists. BUS for NEC evaluation has been available at CMKC since 2015. Despite its availability, current use of BUS for NEC evaluation at CMKC remains highly variable, often dependent upon the individual preferences of the treating neonatologist.

32.2 The NICU at KUMC is a 32-bed level III NICU. Majority of infants admitted at the NICU are born at KUMC. Neonatology coverage at KUMC is provided by CMKC neonatologists who are also in-house 24/7. As a general adult hospital, radiology staff at KUMC are composed primarily of adult sonographers and adult radiologists. Currently, only one radiologist at KUMC has the expertise to perform BUS for NEC evaluation. Because of this limited availability, BUS for NEC evaluation is infrequently performed at KUMC. However, as part of our study's aim of investigating

generalizability of BUS in NICUs of adult hospitals, pre-study training will be done to standardize performance and availability of BUS between CMKC and KUMC.

32.3 Close research collaboration exists between the NICUs of CMKC and KUMC. Several research protocols done at CMKC are also done at KUMC. In fact, KUMC is such an active site for collaborative research that a CMKC-employed neonatology research coordinator ([name]) is dedicated solely for recruitment of participants at KUMC-NICU. Although KUMC has its own IRB, majority of the research done at KUMC NICU is approved via reliance on the IRB at CMKC.

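### McNemar's test is planned for paired 5-point ratings with no cut-point; it discards ordinal information and tests only net direction, while Aim 1 hypothesises change without a direction

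*Combined protocol and SAP*

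**What the plan says.** Section 11.0 gives the purpose of the surveys: "We will conduct two surveys to determine change in clinician's diagnostic and therapeutic thinking". Answers are given "using a 5-point Likert scale", anchored by how likely something is. The post-AXR survey covers every infant. The second does not: "The second survey (post-BUS survey), applicable only to infants randomized to AXR + BUS, will be conducted after BUS is performed". Pairs therefore exist only in the AXR + BUS arm.

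Section 28.1 names one analysis for these pairs: "two-tailed McNemar's test with paired measures to analyze differences in diagnostic thinking efficacy and therapeutic efficacy", using the surveys before and after BUS. No section turns five levels into two, defines either kind of efficacy as a yes/no variable, shows the survey items, or plans an ordinal analysis.

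The Study Summary, under Aim 1, states: "We hypothesize that adding BUS to NEC evaluation changes differential diagnosis, therapy plan and patient outcomes". No direction is given.

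**The concern.** Three features of the plan do not fit together.

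- **Scale.** McNemar's test works on a binary variable. As written it cannot be run until someone chooses a cut-point, and nothing prevents that choice from being made after the data are seen.
- **Lost information.** Once a cut is made, a move from 1 to 3 or from 4 to 5 may count as no change.
- **Question.** The test asks whether upward crossings outnumber downward ones. The Aim 1 hypothesis is that diagnosis and plan change. If an item asks how likely NEC is, a useful imaging test would raise the rating in some infants and lower it in others, and those moves offset each other.

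At stake is a non-significant survey result being read as BUS leaving clinicians' thinking unchanged. Diagnosis and therapy plan are the first two effects named in the Aim 1 hypothesis.

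**Working it through.** **The plan's own figure.** The only sample-size calculation is Table 1, for days to full feeds. Total N = 4[SD(1.960 + 0.842)/difference]². For 5 days and SD 8 this gives 4(8 × 2.802/5)² = 80.4, against 81 stated. The other eight cells also reproduce within rounding. Table 1 says nothing about the surveys: no power, discordance rate or number of pairs is given for them.

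**Number of pairs.** Assume an even split and one pair per episode or infant.
- Section 28.3, 67 to 81 episodes: about 34 to 40 pairs.
- Addendum B, 80 infants: 40 pairs.
- Section 8.0, 200 neonates: 100 pairs.

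Alpha of 0.05 is stated for patient outcomes and assumed here for the surveys.

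**Balanced movement.** With b upward and c downward crossings, the exact two-sided P is min(1, 2·Pr[X ≤ min(b, c)]), X ~ Binomial(b + c, 0.5).
- 8 up, 8 down: 2 × 0.598 exceeds 1, so P = 1.0, with 16/40 = 40% of pairs crossing.
- 12 up, 8 down: P = 0.50.
- 15 up, 5 down: P = 0.041.

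Probability of rejection with the exact test, when half of all pairs cross the cut:

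| Up / down | 34 pairs | 40 pairs | 100 pairs |
|---|---|---|---|
| 25% / 25% | 3% | 3% | 4% |
| 30% / 20% | 9% | 10% | 25% |
| 40% / 10% | 66% | 74% | 99% |

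**Movement on one side of the cut.** In a simulation with the cut at 4 or above and moves only 1 to 2, 2 to 3 or 4 to 5, about 36% of pairs changed. McNemar rejected in 0% of runs and the signed-rank test in 100%, at 40 and at 100 pairs.

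**One-way shift.** Assume latent ratings X ~ N(0, 1) and Y = 0.4 + 0.7X + √(1 − 0.49)·e with e ~ N(0, 1), both cut into five categories. With equal-frequency categories, the boundary for 4 or above is 0.253. Then Pr(up) = 22.0% and Pr(down) = 6.2%, and summing the exact test over the number of crossings gives power of 30%, 37% and 83% at 34, 40 and 100 pairs. With boundaries at ±0.5 and ±1.5, the crossing rates are 21.1% and 5.9% and power is 28%, 35% and 81%. Over the spacings tried:

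| Pairs | Exact McNemar, cut at 4 or above | Signed-rank |
|---|---|---|
| 34 | about 25-30% | about 70% |
| 40 | about 33-38% | about 77-79% |
| 100 | about 77-83% | about 99% |

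Moving the cut to 3 or above lowers McNemar to about 29-31% at 40 pairs. The uncorrected chi-square version reaches about 40-46% there. The result therefore depends on a cut-point and a test version that the plan does not state.

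**What the signed-rank test does not cure.** When movement was simulated in both directions, with 54% of pairs changed, it rejected in 5% of runs and McNemar in 3% to 7%.

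**What a simple proportion changed does not show.** In the same latent model with equal-frequency categories, about 60% of pairs change by one or more categories with zero shift and about 62% with the 0.4 SD shift. For two or more categories the figures are about 20% and 24%. Even at correlation 0.9 with zero shift, about 43% change by one or more.

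**The case against.** The strongest defence is section 2.2, which speaks of BUS changing diagnosis and plan favourably. A test of net direction is coherent if the items are worded so that favourable always means the same end of the scale. The items are not shown, so this cannot be excluded, and the cancellation argument is conditional on an item such as the likelihood of NEC. The missing cut-point and the discarded categories remain either way.

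It is also fair that a clearly one-sided shift would be found (40% against 10% gives 74% power at 40 pairs), that 100 pairs largely restore McNemar's power for the assumed shift, and that no survey power is claimed.

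Three stronger readings are tempting, and the documents do not support them.

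- **McNemar would show nothing.** That is true only when crossings are about balanced.
- **Repeat raters inflate the type I error by a known amount.** Section 32.2 says "Neonatology coverage at KUMC is provided by CMKC neonatologists", so repeat raters are likely. But the number of raters is not given, and section 8.0 lists 200 neonatologist participants, one per neonate, which may count responses rather than people. No error rate can be derived.
- **A high proportion of changed ratings would demonstrate a BUS effect.** The AXR arm has no second rating, so there is no comparator and no null value, and re-rating noise alone can produce a large proportion.

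**Conclusion.** The concern holds as a mismatch between scale, test and hypothesis. The planned analysis is incomplete without a cut-point, ignores movement within either side of it, and addresses only net direction. At 34 to 40 pairs, the cost for a moderate one-way shift is roughly half the power; at 100 pairs it is about 16 to 22 percentage points (99% less 77-83%). These sizes rest on an assumed 0.4 SD shift, correlation 0.7, assumed category spacing, an even split and one pair per infant or episode. The cancellation point rests on unseen item wording. The finding affects only the survey part of Aim 1, not the patient-outcome comparisons. It does not mean that McNemar's test is invalid once a cut-point is fixed.

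**What to change.** In section 28.1:

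1. Test direction on the full 5-point scale with the Wilcoxon signed-rank test, separately for diagnosis and therapy items. A cumulative-link mixed model with a random effect for neonatologist is an alternative if a rater code is kept.
2. Report descriptively the 5x5 transition table and the proportion of pairs changing by one or more and by two or more categories, in each direction, with 95% confidence intervals. State that no AXR-only second rating exists, so these proportions include re-rating noise and do not test a BUS effect.
3. Keep McNemar only as a supportive analysis, with the cut-point and the test version fixed before the data are seen.

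The cost is revised analysis wording and slightly more analysis work on the same surveys. The mixed model also needs a rater code stored with each survey. Item 1 does not recover balanced two-way change, which is why item 2 is needed beside it.

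### Section 28.1 censors death in the full-feeds curve, no section compares deaths by arm, and 25.1-25.3 stop feeding data after withdrawal despite an intention-to-treat analysis

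*Combined protocol and SAP*

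**What the plan says.** Days to full feeds is analysed twice in 28.1. First, "Comparison of duration of antibiotics, bowel rest, and days to full enteral feeds will be performed using Student's t-test". Second, a Kaplan-Meier curve is drawn by group, "censoring for death, discharge/transfer out of the hospital, or 30 days following initial NEC concern". No test is named for the curve, and no rule says what the t-test does with an infant who has no full-feeds date. The same paragraph states that "Analyses of patient outcomes (duration of bowel rest, duration of antibiotics, time to full feeds) will follow the intention-to-treat principle". Section 28.3 sizes the trial on mean days to full feeds.

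Death is not among the patient outcomes named in 28.1. Section 12.0 lists "clinical outcomes at discharge (total length of stay, age at discharge, co-morbidities during NICU admission" without naming death, and the data list in 26.1 omits it. Its date is recorded under 24.2. Section 31.0 marks data monitoring for safety as not applicable.

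On withdrawal, 25.1 allows it on transfer to an outside hospital, or "if they undergo exploratory laparotomy with ostomy and mucus fistula creation during the course of their admission", giving the reason "as this procedure can preclude them from safely undergoing a BUS". Section 25.2 adds: "Subjects may also be discontinued from the study at the discretion of the site investigator as deemed appropriate for any reason". Under 25.3, only safety information is collected after that. For all other infants, 12.0 says "Follow-up will end once infants are discharged from the NICU".

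**The concern.** There are two separate problems.

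First, censoring treats a dead infant as one who might still have reached full feeds later. One minus the Kaplan-Meier estimate is then the share that would reach full feeds if nobody died, which is higher than the share that does. If deaths differ by arm while feeding speed does not, the curves coincide although the true shares differ. With no count of deaths by arm planned, nothing else in the analysis would show it. Section 1.0 calls the disease life-threatening, so deaths must be expected.

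Second, an intention-to-treat comparison needs the outcome of withdrawn infants. Those withdrawn after an ostomy are likely to be slow to reach full feeds. If they are lost unevenly between the arms, the t-test on the outcome that sizes the trial is biased towards the arm that loses more of them.

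**Working it through.** **The plan's own figure.** Total N = 4(1.960 + 0.842)² × SD²/difference². For SD 8 and 5 days this is 80.4, rounded up to the 81 in Table 1. The sample-size arithmetic is not at issue.

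**Inputs.** Mean 16, SD 9 days (28.3); day-30 limit (28.1); target of 80 infants (Addendum B), taken as 40 per arm. Assumptions: lognormal feeding time T (log-mean 2.635, log-SD 0.524), a constant death hazard h independent of T, 1:1 allocation, two-sided 0.05. Death and ostomy rates are not in the documents.

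**Overstatement by the curve.** With death censored, one minus Kaplan-Meier at day 30 estimates P(T ≤ 30) = 92.8%, whatever the mortality. The true share is the integral of f(t)exp(−ht) from 0 to 30, with h chosen so that the stated percentage die before full feeds by day 30.

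| Die first | h per day | True share | Overstatement |
|---|---|---|---|
| 2% | 0.0013 | 91.1% | 1.7 points |
| 5% | 0.0034 | 88.5% | 4.3 points |
| 10% | 0.0069 | 84.2% | 8.6 points |
| 15% | 0.0108 | 79.8% | 13.0 points |

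A gamma shape gives 1.7, 4.3, 8.6 and 12.9 points.

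**Effect on the arm comparison.** With equal death hazards (5%) and true means of 16 and 11 days, the gap between arms at day 14 is 25.3 points by Kaplan-Meier and 25.2 by cumulative incidence; at day 30 it is 3.3 and 4.5. With equal mortality the comparison is little affected.

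**Unequal deaths.** I simulated 4,000 trials with no feeding effect, 40 per arm and 5% vs 15% deaths. A death-censored log-rank test (an illustration, since 28.1 names no test) rejects in 5.3% of trials, a Gray-type test that keeps deaths in the risk set in 13.1%, and Fisher's exact test on deaths in 17.5%. A simple comparison of deaths shows the difference best, and even that has low power.

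**Withdrawal, assumed worst case.** A proportion p is lost from one arm only, all from the slowest 30% of feeders, whose mean is 26.66 days. The mean of those kept is (16 − 26.66p)/(1 − p):

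- p = 5%: 15.4 days, bias 0.6
- p = 10%: 14.8 days, bias 1.2
- p = 15%: 14.1 days, bias 1.9

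At 40 per arm with no true effect, the t-test then rejects in about 6%, 8-9% and 16% of trials.

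**How long to keep reading charts.** The t-test has no day-30 limit. Of the slowest 30%, 0.072/0.30 = 24% exceed day 30, with mean 38.77 days. If reading stopped at day 30, these infants would stay missing. With p' = 0.24p, the remaining bias is 16 − (16 − 38.77p')/(1 − p') = 0.28, 0.56 and 0.85 days, nearly half of the original. Reading must therefore run to NICU discharge.

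**The case against.** The case for the plan is substantial. A death-censored curve is a recognised estimate of the feeding rate among infants alive and in hospital. A reader might infer that the plan confuses slower feeding with more deaths. It does not: that curve separates them, and it is the cumulative incidence curve that combines them. Death is not ignored in data capture either. Section 24.2 records its date, the censoring rule needs that date, and the safety exception in 25.3 plausibly covers deaths after withdrawal. The absence of safety monitoring in 31.0 says nothing about the final analysis.

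A reader might also infer that infants with an ostomy will be lost from the AXR + BUS arm only. The documents do not say so: 25.1 is permissive and names no arm. Its reason concerns the safety of BUS, which the AXR arm receives only by cross-over, expected to be rare (10.5). Uneven loss is therefore possible but not established. Nor does the enrolment goal of 200 infants in 8.0 support a 100-per-arm calculation, because the form defines it as infants consented or screened.

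All of that stands. It leaves three gaps: the curve cannot be read as the share reaching full feeds, deaths are not compared by arm, and feeding data stop at withdrawal.

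**Conclusion.** The point holds and should be fixed. Once any infant dies before full feeds, one minus the planned curve is too high; that direction is certain. The size rests on assumed death rates: under 2 points if 2% die first, 13 if 15% do. With equal mortality the arm comparison is little affected; with unequal mortality the difference could go unreported.

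The conflict between 25.1-25.3 and the intention-to-treat statement is plain on the text. The resulting bias of about 0.6-1.9 days is a worst case resting on three assumptions: loss in one arm only, 5-15% lost, and all of them from the slowest 30%. For scale, 28.3 plans to detect 5 to 6 days.

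**What to change.** 1. In 28.1, present the cumulative incidence of full feeds to day 30 by arm, with death as a competing event, as the estimate of the share reaching full feeds. Label any death-censored curve that is kept as the feeding rate among infants alive and in hospital.
2. Report by arm the number of deaths, with a simple comparison such as Fisher's exact test, and the number of infants without a full-feeds date by reason (death, transfer, discharge, withdrawal under 25.1 or under 25.2). Keep the t-test, labelled as conditional on reaching full feeds.
3. In 25.3, state that full-feeds, bowel-rest, antibiotic and death dates are still read from the chart to NICU discharge, in both arms, for infants withdrawn from study imaging under 25.1 or 25.2 who remain in the NICU. This changes data collection only and leaves the clinical reasons for withdrawal as they are.

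The cost is wording, a little more chart review and one more analysis. The incidence curve combines feeding speed with survival, so it needs the death counts beside it. At about 80 infants, power for a mortality difference is low, and the comparison of deaths should be presented as descriptive support.
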